a) Change in medications that alter potassium homeostasis (e.g., RAAS inhibitors, diuretics, β -blockers) in the last month

b) Diagnosed with bowel diseases or syndromes (e.g., bowel obstruction, major GI surgery, short-bowel syndrome, irritable bowel syndrome, inflammatory bowel disease, chronic diarrhea)

c) Dietary restrictions (e.g., allergies) or otherwise unable/unwilling to adhere to study diets (excludes dietary restrictions on high-potassium foods)

d) Pregnant (females) or planning to become pregnant (males and females) during the study

If at any point during the study (including baseline) a participant has moderate-severe hyperkalemia (potassium \geq 6.5mEq/L), or if a participant becomes pregnant during the study, they will be withdrawn from the study.

Inclusion of women and minorities

Given the pilot nature of the intervention and small sample size (n=10), the study population will not be representative of the CKD population, and will have insufficient power to detect differences in intervention effects by sex and race/ethnicity. To our knowledge, plant-rich diets, such as those being investigated in this study, have similar health effects by sex and race/ethnicity. No individual will be excluded from the study on the basis of sex or race/ethnicity alone, and we will attempt to obtain a sample that reflects the demographics of our source population.

5) Study-Wide Number of Subjects

We will recruit a total of 10 individuals to the study. We have secured the support of the New York Harbor VA Healthcare System, which served approximately 250 non-dialysis CKD patients in the New York City area, as well as the Division of Nephrology at NYU Langone Health. It is estimated that approximately 10% of these patients have hyperkalemia. Thus, we have no concerns about our ability to access and recruit the required number of participants for this study. The estimate demographic breakdown of patients at the renal clinic are 95% male with 40% white, 25% black, 20% Hispanic, 10% Asian, and 5% other racial/ethnic background. The planned enrollment is outlined in Table 1.

Table 1. Planned enrollment report

Racial Categories	Ethnic Categories				Total
	Not Hispanic or Latino		Hispanic or Latino		
	Female	Male	Female	Male	
American Indian/ Alaskan Native	0	0	0	0	0
Asian	0	1	0	0	1
Native Hawaiian or Other Pacific Islander	0	0	0	0	0
Black or African American	0	2	0	1	3
White	1	3	0	1	5

More than 1 race	0	1	0	0	1
Total	1	7	0	2	10

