6) Study-Wide Recruitment Methods

Potential participants will be identified using two recruitment methods: 1. Referral by the patient's nephrologist, and 2. DataCore directed search of electronic medical records. Nephrologist referral patients will be obtained from the New York Harbor VA Healthcare System, NYU Langone Health, and Bellevue Hospital. The DataCore directed search of electronic medical records will be limited to patients of nephrologists in the Division of Nephrology who have an episode of mild hyperkalemia in the past 6-months. Once identified using the electronic medical record search, the patient's nephrologists will be notified about their potential eligibility. Per the study inclusion criteria, nephrologists will be asked to confirm that the patient is appropriate for the study.

- (a) [name] or [name] will review each section of the written consent form with the referred participant, ask the participant if they understand each section, and clarify any questions they may have. The participant and the person obtaining consent will sign and date the consent form. Copies of the consent, which includes the contact information of the PI ([name]), will be provided to the participant and sent to the patient's nephrologist. Informed consent will be considered an ongoing process throughout the study, and participants' questions regarding their rights and responsibilities will be addressed whenever they occur.
- (b) Once enrolled, [name] and [name] will meet to verify that the participant meets the inclusion/exclusion criteria. This information will be obtained from the patient's electronic medical record.
- (c) Study staff will contact eligible patients, and schedule a fasting screening appointment (at least 8 hours of fasting).

A fasting blood sample will be obtained at the screening visit, and analyzed for potassium. If this test is in the range of mild hyperkalemia (potassium 5.1 to <6.5 mEq/L), the participant will be deemed to have persistent hyperkalemia, and be accrued. Otherwise they will be deemed ineligible, and excluded from the study. Regardless of enrollment status, all eligible patients who are invited to participate in the study will be reimbursed \$25.00 for time and travel expenses incurred by attending the screening visit.

7) Study Timelines

We will recruit 10 participants. Given the intensiveness of the intervention, no more than two participants will be enrolled in the intervention at a time.

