Once half of the participants are enrolled and accrued, the PI ([name]) will review serum potassium concentrations to ascertain if there were any episodes of moderate-severe hyperkalemia, or protocol issues that require reporting, withdrawing a participant and/or stopping the study. An AE is any unfavorable and unintended sign, symptom, or disease, including worsening of pre-existing medical conditions. The criteria for withdrawing participants are outlined in section 14 below. The study will be stopped if there is a serious adverse event (SAE) related to the study. Any SAE related to the intervention will be reported to the NYU School of Medicine Institutional Review Board by phone and email within 24-hours of being notified. To minimize participant risk and facilitate monitoring, we plan to enroll cohorts of ≤ 2 participants rather than a single cohort of 10 participants. Summary data and safety monitoring reports will be submitted to the NYU School of Medicine Institutional Review Board during annual review, or if there are changes in the risk/benefit ratio of the study.

As per our Clinical Trial Agreement with Relypsa, Inc., the PI will undergo training in reporting AEs by Relypsa, Inc. before starting the study, and will report all AEs that occur after the signing of informed consent, and up to 14 days after the intervention to the Drug Safety and Pharmacovigilance (DSPV) Department at Relypsa, Inc within 15 days of completing the study. Any AEs that are considered serious (SAEs), which occur will be reported to Relypsa, Inc. DSPV Department within 24-hours of being identified/reported. SAE include “any untoward medical occurrence that at any dose: (i) results in death; (ii) is immediately life threatening (i.e. in the opinion of the investigator, the AE places the subject at immediate risk of death; it does not include a reaction that, had it occurred in a more severe form, might have caused death); (iii) requires inpatient

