hospitalization or results in prolongation of an existing hospitalization; (iv) results in a persistent or significant incapacity or substantial disruption of the ability to conduct normal life functions; (v) is a congenital anomaly or birth defect; or (vi) is an important medical event that may not be immediately life threatening, result in death, or require hospitalization, but may be considered an SAE when, based upon appropriate medical judgment, it jeopardizes the subject or may require medical or surgical intervention to prevent one of the outcomes listed in subsections (i) – (v)” (defined per the Clinical Trial Agreement with Relypsa, Inc.).

This study investigates the use of patiomer for managing normal serum potassium concentrations in CKD patients who are transitioned to a plant-rich diet. The major risk to participants in this study is cardiotoxicity related to hyperkalemia. Patiomer has been demonstrated to be effective for lowering serum potassium concentrations and keeping them in the normal range in CKD patients with hyperkalemia, but the role of dietary potassium on serum potassium concentrations is unclear. Current dietary guidelines for managing hyperkalemia in CKD patients recommend avoiding high-potassium plant foods; however, this long-standing practice has never been demonstrated to be necessary, and may contribute to other disease complications⁴. To our knowledge, this is the first study to evaluate liberalizing the diets of CKD patients with hyperkalemia, so we have incorporated many design features that can help us to protect against this risk.

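### Section 12 schedules one early potassium review, and a confirmed potassium of 6.5 mEq/L or more that is judged not to be a related SAE triggers no required study-level review before others start or move to the high-potassium diet

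*Combined protocol and SAP*

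**What the plan says.** **Study level.** Section 12 (Provisions to Monitor the Data to Ensure the Safety of Subjects) sets one PI review of serum potassium: "Once half of the participants are enrolled and accrued". Its purpose is to find "any episodes of moderate-severe hyperkalemia, or protocol issues that require reporting, withdrawing a participant and/or stopping the study". The one automatic stop is separate: "The study will be stopped if there is a serious adverse event (SAE) related to the study". Section 12 also sends safety reports to the IRB at annual review or when the study's risk/benefit ratio changes.

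**When accrual occurs.** Under section 6 (Study-Wide Recruitment Methods), a screening potassium in the mild range means that "the participant will be deemed to have persistent hyperkalemia, and be accrued". Accrual therefore comes before any patiromer or study diet.

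**Participant level.** Section 4 says of participants whose potassium reaches 6.5 mEq/L or more that "they will be withdrawn from the study". Under Table 2 in section 9, every value above 6.0 goes to the study nephrologist, and section 12 adds a confirmatory blood test. The last limb of the SAE definition covers an important medical event that "may be considered an SAE when, based upon appropriate medical judgment, it jeopardizes the subject or may require medical or surgical intervention".

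**Staggering.** Section 12 gives the reason for small cohorts: "To minimize participant risk and facilitate monitoring, we plan to enroll cohorts of" two or fewer. Section 7 adds that "no more than two participants will be enrolled in the intervention at a time".

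**The concern.** Section 12 names hyperkalemia-related cardiotoxicity as the major risk and describes this as the first study to liberalize the diets of CKD patients with hyperkalemia. Small cohorts protect later participants only if what happens in one cohort is considered before the next is exposed. The plan makes that consideration mandatory once, on a date fixed by accrual rather than by an event.

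After a confirmed potassium of 6.5 or more that is judged not to be a related SAE, two exposures can go ahead with no required study-level decision: the start of further participants, and a concurrent cohort-mate's move from the low-potassium phase I diet to the phase II diet. Whether they go ahead is left to discretion that need not be recorded.

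**Working it through.** **1. What each provision acts on**

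| Provision | Acts on | Required before further exposure of others? |
|---|---|---|
| Withdrawal at 6.5 or more (section 4) | the individual | no |
| Nephrologist contact and repeat test (Table 2; section 12) | the individual | no |
| Related-SAE stop (section 12) | the study | yes, if judged a related SAE |
| IRB report on changed risk/benefit (section 12) | the study | no potassium trigger, no hold |
| PI potassium review (section 12) | the study | once, at half accrual |

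**2. Timing of the review**

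Ten participants in full pairs make 10/2 = 5 pairs and 4 between-pair transitions. Half is 5 participants, and the fifth is in pair 3. Because accrual is at screening, a review held promptly has on-study data from participants 1-4 at most. Participants 5-10 then have no scheduled study-level review of their on-study values. Each pair is on study for 4 weeks, so an event in pair 1 could wait through the whole of pair 2.

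**3. How often a start could follow an event with no required review**

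The protocol states no figure to reproduce and no rate of potassium at or above 6.5. Assumptions: five sequential pairs; independent events at rate p per participant; no replacement; a share s of events judged related SAEs, which stop the study. Pair 5 is not counted, because nobody starts after it.

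- Review between pairs 2 and 3: events in pairs 1, 3 and 4 (6 participants) are uncovered.
- Review between pairs 3 and 4: events in pairs 1, 2 and 4 (again 6) are uncovered.
- Review while pair 3 is on study: it is too late for the start of pair 3 and may precede pair 3's own events, so up to 8 participants (pairs 1-4) are uncovered.

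With s = 0 the chance is 1 - (1 - p)^6 or 1 - (1 - p)^8. For example, at p = 5%, 1 - 0.95^6 = 0.265 and 1 - 0.95^8 = 0.337.

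With s > 0, let q = (1 - p)^2 (no event in a pair), c = (1 - ps)^2 (no related SAE in a pair) and n = c - q (at least one event, none a related SAE). The chance is:

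- review before pair 3: n + qc(n + qn)
- review before pair 4: n + qn + q²cn
- review during pair 3: n(1 + q + q² + q³)

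For example, at p = 10% and s = 0.5, q = 0.81, c = 0.9025 and n = 0.0925, which gives 0.215, 0.222 and 0.277.

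| Share judged related SAEs | Review position | p = 1% | 2% | 5% | 10% |
|---|---|---|---|---|---|
| none | between pairs | 5.9% | 11.4% | 26.5% | 46.9% |
| none | during pair 3 | 7.7% | 14.9% | 33.7% | 57.0% |
| half | between pairs | 2.9% | 5.6% | 12.7-12.9% | 21.5-22.2% |
| half | during pair 3 | 3.9% | 7.4% | 16.6% | 27.7% |
| nine in ten | between pairs | 0.6% | 1.1% | 2.4-2.5% | 4.0-4.3% |
| nine in ten | during pair 3 | 0.8% | 1.5% | 3.3% | 5.4% |

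The table counts new starts only; a cohort-mate's move to phase II is not included.

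**The case against.** The best defence is that a stop-relevant judgment already attaches to each event. The AE definition includes worsening of an existing condition, so an on-study potassium of 6.5 or more is an AE. SAEs must reach the manufacturer within 24 hours of being identified or reported, and related SAEs must reach the IRB within 24 hours of notification. Those deadlines imply prompt assessment of seriousness and relatedness, and a related SAE ends the study. The study nephrologist prescribes patiromer for everyone and appears to be the PI (sections 9 and 21), so nobody is likely to start without a prescription from someone who knows of the event. What remains, on this view, is record-keeping in a ten-person proof-of-concept study.

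Much of this stands. A reader might infer from section 12 that stopping is considered only once, or that a value of 6.5 or more goes unheeded. The documents do not support either inference.

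It does not close the point. Deciding that one participant's event is not a related SAE is a classification of that event. It does not require anyone to look across participants' potassium data or to decide whether others should be exposed. The last SAE limb depends on medical judgment, and the IRB clause has no potassium trigger.

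Two smaller objections are fair. Grammatically, the requirement to stop could attach only to protocol issues; the natural reading includes hyperkalemia episodes, since the potassium review exists to find them. And "pair" is a simplification: the text allows single participants or rolling starts. Neither reading adds a required review.

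**Conclusion.** The gap is real but small. The one scheduled review can fall before participant 5 has on-study data, and none follows. A confirmed potassium of 6.5 mEq/L or more judged not to be a related SAE therefore prompts no required study-level decision, and cohorts of two or fewer do not fully deliver the monitoring purpose stated for them.

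The size depends on two quantities that the documents do not give: the event rate and the share of events judged related SAEs. With that share at zero, the chance that a start follows an event without a required review is about 6% to 47% (review between pairs), or up to 8% to 57% (review during pair 3), over assumed rates of 1% to 10%. If nine in ten events are judged related SAEs, it falls to between about 0.6% and 5%. Given the risk that the protocol names, a high share is plausible. The percentages show how often a hold would apply. A reader might take them as harm that a hold would avert, but nothing in the documents allows that estimate. This is a cheap improvement, not a design failure.

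**What to change.** Add one sentence to section 12: any confirmed on-study potassium of 6.5 mEq/L or more holds new starts, and any concurrent participant's move to the phase II diet, until the PI has reviewed all potassium data to date and recorded a decision to continue, modify or stop. Keep the midpoint review and the related-SAE stop as they are.

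The cost is a possible brief pause. No new visit, assay or committee is needed: potassium is already measured weekly, and the PI already has the safety-monitoring role. A participant leaves at the first such event, so the sentence triggers at most one review per affected participant. The expected number over the study is at most 10p, that is 0.1, 0.2, 0.5 and 1.0 at assumed rates of 1%, 2%, 5% and 10%.
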